14.1 Demographic Data			
14.1.1	Subject Enrollment and Disposition	All Populations	U
14.1.2	Study Visits	ITT	U
14.1.3	Protocol Deviation by Site	ITT	U
14.1.4	Demographic and Baseline Characteristics	ITT	U
14.1.5	All Medical History	ITT	U
14.1.6	Cosmetic/Aesthetic Procedures and Implant History	ITT	R
14.1.7.1	Prior Medications by WHO Drug Dictionary ATC-3 Code and Preferred Name	ITT	U
14.1.7.2	Concomitant Medications by WHO Drug Dictionary ATC-3 Code and Preferred Name	ITT	R
14.1.7.3	Concomitant Medications by WHO Drug Dictionary ATC-3 Code and Preferred Name, Started Due to a Related AE	ITT	R
14.1.8.1	Summary of Concomitant Procedures/Treatments	ITT	R
14.1.8.2	Summary of Concomitant Procedures/Treatments Started Due to an AE	ITT	R
14.2 Efficacy Data			
14.2.1.1	Composite Responder Rates by Treatment using the GL-ILA/GL-SLA at Month 1 (MI)	mITT	U
14.2.1.2	Composite Responder Rates by Treatment using the GL-ILA/GL-SLA at Month 1 (BOCF)	mITT	R
14.2.1.3.1	Composite Responder Rates by Treatment using the GL-ILA/GL-SLA at Month 1 (OC)	ITT	R
14.2.1.3.2	Composite Responder Rates by Treatment using the GL-ILA/GL-SLA at Month 1 (OC)	PP	R
14.2.1.3.3	Composite Responder Rates by Treatment using the GL-ILA/GL-SLA at Month 1 (OC)	Safety	R
14.2.1.3.4	Composite Responder Rates by Treatment using the GL-ILA/GL-SLA at Month 1 (OC)	mITT	R
14.2.1.4	Composite Responder Rates by Age using the GL-ILA/GL-SLA at Month 1 (MI)	mITT	U
14.2.1.5	Composite Responder Rates by Site using the GL-ILA/GL-SLA at Month 1 (MI)	mITT	U
14.2.1.6	Composite Responder Rates by Fitzpatrick Skin Type using the GL-ILA/GL-SLA at Month 1 (MI)	mITT	R
14.2.1.7	Composite Responder Rates by Gender using the GL-ILA/GL-SLA at Month 1 (MI)	mITT	R
14.2.1.8	Composite Responder Rates by Baseline GL-ILA at Maximum Frown using the GL-ILA/GL-SLA at Month 1 (MI)	mITT	R

Effective date: 2021-02-05 13:16

Effective

Version: 1.0

Table Number	Table Title	Analysis Population	(U)nique/ (R)epeat
14.2.1.9	Composite Responder Rates by Prior Botulinum Toxin Use using the GL-ILA/GL-SLA at Month 1 (MI)	mITT	R
14.2.1.10	Composite Responder Rates by Type of Month 1 Visit using the GL-ILA/GL-SLA at Month 1 (OC)	ITT	R
14.2.1.11	Composite Responder Rates by Treatment using the GL-ILA/GL-SLA at Maximum Frown at Each Visit (OC)	ITT excluding remote assessments at that visit	U
14.2.2.1	Composite Responder Rates by Treatment using the LCL-ILA/LCL-SLA at Month 1 (MI)	mITT	U
14.2.2.2	Composite Responder Rates by Treatment using the LCL-ILA/LCL-SLA at Month 1 (BOCF)	mITT	R
14.2.2.3.1	Composite Responder Rates by Treatment using the LCL-ILA/LCL-SLA at Month 1 (OC)	ITT	R
14.2.2.3.2	Composite Responder Rates by Treatment using the LCL-ILA/LCL-SLA at Month 1 (OC)	PP	R
14.2.2.3.3	Composite Responder Rates by Treatment using the LCL-ILA/LCL-SLA at Month 1 (OC)	Safety	R
14.2.2.3.4	Composite Responder Rates by Treatment using the LCL-ILA/LCL-SLA at Month 1 (OC)	mITT	R
14.2.2.4	Composite Responder Rates by Age using the LCL-ILA/LCL-SLA at Month 1 (MI)	mITT	U
14.2.2.5	Composite Responder Rates by Site using the LCL-ILA/LCL-SLA at Month 1 (MI)	mITT	U
14.2.2.6	Composite Responder Rates by Fitzpatrick Skin Type using the LCL-ILA/LCL-SLA at Month 1 (MI)	mITT	R
14.2.2.7	Composite Responder Rates by Gender using the LCL-ILA/LCL-SLA at Month 1 (MI)	mITT	R
14.2.2.8	Composite Responder Rates by Baseline LCL-ILA at Maximum Smile using the LCL-ILA/LCL-SLA at Month 1 (MI)	mITT	R
14.2.2.9	Composite Responder Rates by Prior Botulinum Toxin Use using the LCL-ILA/LCL-SLA at Month 1 (MI)	mITT	R
14.2.2.10	Composite Responder Rates by Month 1 Visit Type using the LCL-ILA/LCL-SLA at Month 1 (OC)	ITT	R
14.2.2.11	Composite Responder Rates by Treatment using the LCL-ILA/LCL-SLA at Maximum Smile at Each Visit (OC)	ITT excluding remote assessments at that visit	U
14.2.3.1	Responder Rates using the GL-ILA at Maximum Frown at Each Visit	ITT excluding remote assessments at that visit	U

2021-02-05 13:16

Effective date:

Effective

Version: 1.0

Table Number	Table Title	Analysis Population	(U)unique/ (R)epeat
14.2.3.2	Responder Rates using the GL-ILA at Maximum Frown at Each Visit	ITT	U
14.2.3.3	Summary of Number and Percent of Subjects in Each Response Category of GL-ILA at Maximum Frown at Each Visit	ITT	U
14.2.4.1	Responder Rates using the LCL-ILA at Maximum Smile at Each Visit	ITT excluding remote assessments at that visit	R
14.2.4.2	Responder Rates using the LCL-ILA at Maximum Smile at Each Visit	ITT	U
14.2.4.3	Summary of Number and Percent of Subjects in Each Response Category of LCL-ILA at Maximum Smile at Each Visit	ITT	U
CCI			
14.2.6.1	Responder Rates using the GL-SLA at Maximum Frown at Each Visit	ITT	R
14.2.6.2	Summary of Number and Percent of Subjects in Each Response Category of GL-SLA at Maximum Frown at Each Visit	ITT	R
CCI			
14.2.8.1	Responder Rates using the LCL-SLA at Maximum Smile at Each Visit	ITT	R
14.2.8.2	Summary of Number of Percent of Subjects in Each Response Category of LCL-SLA at Maximum Smile at Each Visit	ITT	R
CCI			
14.2.10.1	Percentage of Subjects with ≥ 1 Grade Improvement using the GL-ILA at Maximum Frown at Each Visit	ITT	U
CCI			
14.2.10.3	Percentage of Subjects with ≥ 1 Grade Improvement using the GL-SLA at Maximum Frown at Each Visit	ITT	R

Effective date: 2021-02-05 13:16

Effective

Version: 1.0

 GALDERMA	Title 43QMI902 Statistical Analysis Plan US - QMI114-DP - GL&LCL	Doc id MA-43265	
Table Number	Table Title	Analysis Population	(U)nique/ (R)epeat
14.2.11.1	Percentage of Subjects with ≥ 1 Grade Improvement using the LCL-ILA at Maximum Smile at Each Visit	ITT	U
CCI			
14.2.11.3	Percentage of Subjects with ≥ 1 Grade Improvement using the LCL-SLA at Maximum Smile at Each Visit	ITT	R
CCI			
14.2.12.1	Percentage of Subjects with ≥ 2 Grade Improvement using the GL-ILA at Maximum Frown at Each Visit	ITT	U
CCI			
14.2.12.3	Percentage of Subjects with ≥ 2 Grade Improvement using the GL-SLA at Maximum Frown at Each Visit	ITT	R
14.2.13.1	Percentage of Subjects with ≥ 2 Grade Improvement using the LCL-ILA at Maximum Smile at Each Visit	ITT	R
CCI			
14.2.13.3	Percentage of Subjects with ≥ 2 Grade Improvement using the LCL-SLA at Maximum Smile at Each Visit	ITT	R
CCI			
14.2.14.1	Time to Return to Baseline Score on GL-ILA and GL-SLA at Maximum Frown	ITT	U
14.2.14.2	Time to Return to Baseline Score on GL-ILA and GL-SLA at Maximum Frown for Subjects with ≥ 2 Grade Improvement at Month 1 GL-ILA at Maximum Frown	ITT	R
14.2.15.1	Time to Loss of Grade 0 or 1 on the GL-ILA and GL-SLA at Maximum Frown	ITT	R
14.2.15.2	Time to Loss of Grade 0 or 1 on the GL-ILA and GL-SLA at Maximum Frown for Subjects with ≥ 2 Grade Improvement at Month 1 GL-ILA at Maximum Frown	ITT	R
14.2.16.1	Time to Return to Baseline Score on LCL-ILA and LCL-SLA at Maximum Smile	ITT	U
14.2.16.2	Time to Return to Baseline Score on LCL-ILA and LCL-SLA at Maximum Smile for Subjects with ≥ 2 Grade Improvement at Month 1 LCL-ILA at Maximum Smile	ITT	R

Effective date: 2021-02-05 13:16

Effective date:

Effective

Version: 1.0

Table Number	Table Title	Analysis Population	(U)unique/ (R)repeat
14.2.17.1	Time to Loss of Grade 0 or 1 on the LCL-ILA and LCL-SLA at Maximum Smile	ITT	R
14.2.17.2	Time to Loss of Grade 0 or 1 on the LCL-ILA and LCL-SLA at Maximum Smile for Subjects with ≥ 2 Grade Improvement at Month 1 LCL-ILA at Maximum Smile	ITT	R
CCI			
14.3 Safety Data			
14.3.1 - 14.3.6 Exposure and Adverse Events			
14.3.1	Injection Administration and Characteristics	Safety	U
14.3.2	Overall Summary of Adverse Events	Safety	U

Table Number	Table Title	Analysis Population	(U)nique/ (R)epeat
14.3.3.1	Treatment Emergent Adverse Events by MedDRA System Organ Class and Preferred Term	Safety	U
14.3.3.2	Serious Treatment Emergent Adverse Events by Intensity, MedDRA System Organ Class and Preferred Term	Safety	U
14.3.3.3	Treatment Emergent Adverse Events Related to Study Product or Injection Procedure by Intensity, MedDRA System Organ Class and Preferred Term	Safety	R
14.3.3.4	Treatment Emergent Adverse Events That Led to Discontinuation by Intensity, MedDRA System Organ Class and Preferred Term	Safety	R
14.3.3.5	Treatment Emergent Adverse Events Unrelated to Study Product or Injection Procedure by Intensity, MedDRA System Organ Class and Preferred Term	Safety	R
14.3.3.6	Treatment Emergent Adverse Events Related to Study Product or Injection Procedure by Intensity, MedDRA System Organ Class and Preferred Term by Age	Safety	U
14.3.3.7	Treatment Emergent Adverse Events Related to Study Product or Injection Procedure by Intensity, MedDRA System Organ Class and Preferred Term by Study Site	Safety	U
14.3.3.8	Treatment Emergent Adverse Events Related to Study Product or Injection Procedure by Intensity, MedDRA System Organ Class and Preferred Term by Fitzpatrick Skin Type	Safety	U
14.3.3.9	Treatment Emergent Adverse Events Related to Study Product or Injection Procedure by Intensity, MedDRA System Organ Class and Preferred Term by Race	Safety	U
14.3.3.10	Treatment Emergent Adverse Events Related to Study Product or Injection Procedure by Intensity, MedDRA System Organ Class and Preferred Term by Gender	Safety	R
14.3.3.11	Treatment Emergent Adverse Events Related to Study Product or Injection Procedure by Intensity, MedDRA System Organ Class and Preferred Term by Prior Botulinum Toxin Use	Safety	R
14.3.4	Summary of Duration of Adverse Events Related to Study Product or Injection Procedure by System Organ Class and Preferred Term	Safety	U
14.3.5	Summary of Number of Days to Onset of Adverse Events Related to Study Product or Injection Procedure by System Organ Class and Preferred Term	Safety	R
14.3.6	Summary of Action Taken for Treatment Emergent Adverse Events Related to Study	Safety	U

2021-02-05 13:16

Effective date:

Effective

Version: 1.0

Table Number	Table Title	Analysis Population	(U)nique/ (R)epeat
	Product or Injection Procedure by System Organ Class and Preferred Term		
14.3.7 – 14.3.12 Other Safety			
14.3.7.1	Local Spread of Toxin Events by Intensity, MedDRA System Organ Class and Preferred Term	Safety	U
14.3.7.2	Remote Spread of Toxin Events by Intensity, MedDRA System Organ Class and Preferred Term	Safety	R
14.3.7.3	Hypersensitivity Events by Intensity, MedDRA System Organ Class and Preferred Term	Safety	R
14.3.8	Summary of Hematology Parameters and the Change from Baseline	Safety	U
14.3.9	Summary of Chemistry Parameters and the Change from Baseline	Safety	R
14.3.10	Summary of Vital Sign Parameters and the Change from Baseline	Safety	U
14.3.11	Shift from Baseline in Physical Examination	Safety	U
14.3.12.1	Summary of Electrocardiogram (ECG) Results at Each Visit	Safety	U
14.3.12.2	Electrocardiogram (ECG) Overall Assessment – Shift from Baseline to Each Study Visit	Safety	U
14.3.12.3	Number and Percentage of Subjects with Post-Baseline Abnormal Electrocardiogram (ECG) Results	Safety	U

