7.2.6.2 Reporting Procedures

7.2.6.2.1 Procedures for Reporting Adverse Events

The collection of AEs is from the time that a subject signs the ICF to their final visit.

At each post-enrollment visit, the Investigator (or sub-Investigator) will question the subject about AEs using an open non-persuasive question to elicit reporting of AEs, for example “Have you noticed any change in your health since the last visit?” Directed questioning and examination will then be performed as appropriate.

Any AE occurring during the AE reporting period, whether it is related to the study product or not, will be recorded immediately in the source document, and described on the AE form of the eCRF along with the date of onset, severity, relationship to the study product, and outcome, without omitting any requested and known information. Additional information will be requested under certain circumstances.

 GALDERMA	Title 43QMI902 Clinical Study Protocol - QM1114 - LCL and GL	Doc id MA-40371
--	---	----------------------------------

Effective date: 2020-06-09 07:02

Effective date:

Effective

Version: 4.0

At study end, AEs assessed as related to the treatment or study procedure will be monitored until they have resolved or reached a stable condition. Other AEs will be monitored until the last visit if they have not resolved or reached a stable condition.

The Investigator will maintain all pertinent medical records in the subject's study file. If necessary and approved by the subject or their legal health care representative, the Investigator may contact the subject's personal physician or other health care provider(s) to obtain further details.

For SAEs (see Section 7.2.6.2.2) and pregnancies (see Section 7.2.6.2.3), the Sponsor is to be informed immediately by e-mail. The event must be reported by to the Safety email within 24 hours of receipt of the information (contact details in Section 7.2.6.2.2).

7.2.6.2.2 *Procedure for Reporting a Serious Adverse Event*

For a SAE occurring during the clinical study, regardless of whether it is related to the treatment or not, and of whether it is expected or not, the Investigator must do the following:

1. Take prompt and appropriate medical action, if necessary. The safety of the subject is the first priority.
2. Ensure that the event is classified as an SAE (Section 7.2.6.1.3).
3. Complete the AE form provided in the eCRF as fully as possible.

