Appendix 6 Focused Physical Examination Form Example

Not done Provide details: _____

General Health Assessment

Complete at Screening, Baseline (prior to treatment), Day 7, Day 14, Months 1 and 6/ET

Question the subject about their general health (general wellbeing/ bodily functions, e.g., arms, legs, stomach/ bladder/ bowel, also refer to the list of Adverse Events Potentially Suggestive of Distant Spread of Toxin ([Appendix 7](#))). Abnormalities noted pre-injection should be recorded as medical history and Investigator should confirm if any abnormalities affect subject eligibility. Abnormalities noted post-injection should be documented as AEs.

Next, proceed to the Focused Physical Examination (Part 1 and 2) as indicated below.

Part 1:

Complete at Screening, Baseline (prior to treatment), Day 7, Day 14, Months 1 and 6/ET

Please perform a targeted examination of the face, head, and neck recording abnormalities.

Part 1 Examination	Normal	Abnormal* (provide details)
Eyelid position		
Eyebrow position		
Vision abnormalities (not refractive errors)		
Throat function (e.g., swallowing/drink water)		
Ability to talk and chew		
Ability to stick out and move tongue		
Ability to lift shoulders		

* Abnormal findings at the screening and baseline visit, noted pre-injection, should be recorded as medical history and the Investigator should confirm if any abnormalities affect subject eligibility. Abnormalities noted after study treatment should be documented as AEs.

Investigator Signature

Date

 GALDERMA	Title 43QMI902 Clinical Study Protocol - QM1114 - LCL and GL	Doc id MA-40371
---	--	----------------------------------

PART 2: Complete at Day 7, Day 14, Months 1 and 6/ET

Not done **Provide details:** _____

After questioning the subject about their general health and performing Part 1, determine if there are any **clinically significant abnormalities** that may suggest local or remote spread of toxin effect.

- Local Spread of Toxin Effect refers to effects in areas adjacent to the treatment area (e.g., lower frontalis or medial part of temporalis).
- Remote Spread of Toxin Effect refers to effects in other body parts, not adjacent to the treatment area, when effect can only be attributed to the toxin and there is no other medically sound cause.
- Determine if the event is clinically significant (i.e., would affect subject safety, confound the study data, or requires medical treatment) and document on the source document.

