2.5.2.2 Assessment of local/remote toxin spread and hypersensitivity

Any potential or suspected toxin spread or toxin hypersensitivity events will be evaluated separately. The same methods specified in Section 2.5.2 will be followed. Suspected toxin spread events and suspected hypersensitivity events will be summarized in separate tables. The investigator will conduct the investigation and evaluate if an AE is also a suspected toxin spread or hypersensitivity event; however, Appendix 7 in the CSP lists AEs potentially suggestive of spread of toxin.

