16.2.8 Other Safety Data		
16.2.8.1.1	Hematology Values	U
16.2.8.1.2	Chemistry Values	U
16.2.8.2.1	Physical Examination Findings	U
16.2.8.2.2	Physical Examination, Assessment of Remote/Local Spread of Toxin	U
16.2.8.3	Vital Signs	U
16.2.8.4	ECG Results	U
16.2.8.5	Urine Pregnancy Test	U
16.2.8.6.1	Prior and Concomitant Medications	U
16.2.8.6.2	Concomitant Procedures/Treatments	U

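### SAP 2.5.2.2 fills the hypersensitivity table by investigator judgement alone, with no visible definition, prompt or term list, so Table 14.3.7.3 risks under-counting and site-dependent counting

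*SAP*

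**What the plan says.** SAP section 4.1 lists three special-interest AE tables on the Safety population: local spread of toxin (14.3.7.1), remote spread of toxin (14.3.7.2) and 14.3.7.3, "Hypersensitivity Events by Intensity, MedDRA System Organ Class and Preferred Term". SAP 2.5.2.2 says that suspected spread and suspected hypersensitivity events are summarised in separate tables by the general AE methods, and it names one selector for both: "The investigator will conduct the investigation and evaluate if an AE is also a suspected toxin spread or hypersensitivity event". The only aid to that judgement which it cites is the protocol's Appendix 7; in its words, "Appendix 7 in the CSP lists AEs potentially suggestive of spread of toxin". It gives no definition, preferred-term list or MedDRA query for hypersensitivity.

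Protocol 7.2.6.2.1 requires each AE to be "described on the AE form of the eCRF along with the date of onset, severity, relationship to the study product, and outcome". The two eCRF causality questions (Protocol 7.2.6.1.7, repeated in SAP 1.5.1) ask about the study product and the injection procedure. Part 2 of the Appendix 6 example examination form asks for clinically significant abnormalities "that may suggest local or remote spread of toxin effect".

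**The concern.** One SAP paragraph treats spread and hypersensitivity as parallel, but the protocol prepares the investigator for only one of them. Without a definition or a prompt, whether urticaria, a rash or eyelid swelling is also labelled a suspected hypersensitivity event depends on the individual investigator choosing to apply the label. An omitted label removes the event from Table 14.3.7.3, and no stated step puts it back. The likely error is therefore towards too few events, and the threshold may differ between the up to 15 centers. At stake is the reading of a dedicated safety table for a new protein product: a low count could reflect few events or few labels, and the table as planned would not let a reader tell which.

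**Working it through.** No figure in the plan is in dispute, so there is none to reproduce. The check traces where each judgement is defined, prompted and recorded in the visible text.

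| Step | Toxin spread | Hypersensitivity |
|---|---|---|
| Table planned | SAP 14.3.7.1 and 14.3.7.2 | SAP 14.3.7.3 |
| Selector | Investigator (SAP 2.5.2.2) | Investigator (SAP 2.5.2.2) |
| Directed questioning of subjects | Protocol 1.3; Table 2, footnote 8 | None found |
| Targeted examination | Protocol 7.2.1, local and remote | None found |
| Form item | Appendix 6 Part 2, yes/no for local and for remote | None found |
| Reference list of events | Protocol Appendix 7, cited in SAP 2.5.2.2 | None found |
| Definition or MedDRA search in the SAP | None beyond the Appendix 7 reference | None |

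Next, where the protocol uses the term. Hypersensitivity appears as exclusion criterion 4 (synopsis and section 5.2.2) and in the contraindication note in 7.2.6.1.1. Related wording occurs as illustration: allergy as an example of a chronic disease in 7.2.6.1.1, and allergic bronchospasm as an example of an important medical event in 7.2.6.1.3. None of these asks the investigator to classify a reported AE as a suspected hypersensitivity event. In the visible text that request first appears in the SAP, effective 2021-02-05, after protocol version 4.0 of 2020-06-09.

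Finally, follow one event through the plan. Suppose a subject reports urticaria at the Day 7 visit.

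1. The open question about changes in health elicits it, and it goes on the AE form with onset, severity, relationship and outcome.
2. It is coded in MedDRA and, having started after treatment, is a TEAE (SAP 1.5.1).
3. It is counted by system organ class and preferred term in Table 14.3.3.1, and by intensity in Table 14.3.3.3 if related or 14.3.3.5 if unrelated. It is shown in Listing 16.2.7.1, and in 16.2.7.2 if related.
4. It reaches Table 14.3.7.3 only if the investigator has also labelled it suspected hypersensitivity. No visible instruction or form item prompts that label.

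Steps 1 to 3 are fully specified. Step 4 is not.

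**The case against.** The strongest reply is that absence is being argued from incomplete material. The eCRF and its completion guidance are not in the documents. The AE items in Protocol 7.2.6.2.1 are not offered as a complete list, since the same section adds "Additional information will be requested under certain circumstances". Appendix 6 is labelled an example, the text of Appendix 7 is not visible, and some visit steps and safety wording are redacted. SAP 2.5.2.2 can also be read as describing an assessment that sites already make. This stands: a hypersensitivity field may exist, and it cannot be said that sites are never asked.

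A reader might infer that the table will come out empty and falsely reassure. The documents do not support that. An empty table would require that few or no events are labelled, which is the point that cannot be checked. The events are not hidden either, because a reader can compare Table 14.3.7.3 with the general TEAE tables and AE listings.

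A reader might also infer that spread events get a dedicated listing and hypersensitivity events do not. Listing 16.2.8.2.2, "Physical Examination, Assessment of Remote/Local Spread of Toxin", is a listing of examination findings, not of the AEs selected for Tables 14.3.7.1 and 14.3.7.2. Those tables have no AE listing of their own, so that contrast fails.

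It is tempting to attach a number, such as an upper limit for zero events among all subjects given active product. That would match no planned analysis: the visible SAP gives no confidence interval for AE rates and summarises AEs by treatment group. Both the true rate and the share of events labelled would have to be assumed.

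Finally, investigator judgement is a legitimate way to select events, and hypersensitivity is not a named safety endpoint in Protocol 2.1.4. Both points are fair. They limit the weight of the concern but do not supply the missing definition.

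**Conclusion.** The point holds as a gap in specification. Table 14.3.7.3 depends on one investigator judgement for which the visible protocol and SAP provide no definition, prompt, term list or form item, in contrast to toxin spread. If the plan is followed as written, the table is exposed to under-counting and to differences between sites.

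The size cannot be estimated, because the documents give neither an expected rate nor any information on how often investigators would apply the label. What can be said is the likely direction (too few) and the reach: one descriptive table. The primary analysis, the general TEAE tables and the AE listings are untouched.

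The conclusion assumes that the unseen eCRF and redacted text contain no prompt that would close the gap. If a field with an instruction exists, the under-counting risk shrinks and what remains is that the SAP does not name its source. The change is worth making in either case because it is cheap and makes the count less dependent on the site.

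**What to change.** Before unblinding, amend SAP 2.5.2.2 as follows:

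- Define Table 14.3.7.3 by a fixed list of MedDRA preferred terms, or a standard hypersensitivity query in the MedDRA version used for coding, applied to all TEAEs.
- Add any event that an investigator has flagged as suspected hypersensitivity, whether or not the search finds it.
- Show both counts per treatment arm: events found by the search, and events flagged by the investigator.
- Footnote how events were ascertained, naming the eCRF field and its instruction if they exist, or stating that no such field was collected.

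The cost is a few sentences in the SAP, one term list and one programmed flag on AE data that are to be coded in MedDRA anyway. No site work is needed. The drawback is that a term search will capture some events that are not true hypersensitivity, so the count may look less favourable. Showing the two counts side by side makes that visible.
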